# 11.2.2.2. Optional Observational Substudy

Subjects who complete randomized dosing and who provide consent will be offered an opportunity to participate in an observational substudy. Consenting subjects will be provided an HAE attack diary at the Post-Attack 3 visit and will record details of all HAE attacks that occur for approximately 12 weeks. Resupply of diaries will be provided as needed. Completed diaries should be returned to the site, in person or via mail, approximately every 4 weeks.

Subjects will be provided further instruction on completing the diaries at home for any attacks that occur for subsequent 12 weeks. Subjects will record the occurrence and details of each HAE attack in the diary, beginning from the time of onset of pain or swelling associated with an HAE attack. Subjects will fill out the diary questionnaire and a 3-component VAS at 1, 2, 3, 4, approximately 8 and at 24 hours after the attack started, as well as any medications used since the onset of symptoms.

During Weeks 4, 8, 12 of the observational period, the Investigator (or designee) will phone the subject to discuss completion of the HAE attack diary, collection of completed diaries and whether additional diaries are needed. In addition, AEs assessed as possibly, probably or definitely related to study drug will also be collected. After receipt of the Week 4, 8, 12 diaries, the Investigator (or designee) will review completed HAE diaries for correctness/completeness.

## 12. ASSESSMENT OF SAFETY

# 12.1. Adverse Events

AEs will be assessed and recorded from the time of signing of the informed consent through the appropriate follow-up period. Full details on recording and reporting AEs are provided in Section 12.1.2.

#### 12.1.1. Definitions

#### 12.1.1.1. Adverse Event

An AE is any untoward medical occurrence in a clinical study subject. No causal relationship with the study drug/ IMP or with the clinical study itself is implied. An AE may be an unfavorable and unintended sign, symptom, syndrome, or illness that develops or worsens during the clinical study. Clinically relevant abnormal results of diagnostic procedures including abnormal laboratory findings (e.g, requiring unscheduled diagnostic procedures or treatment measures, or resulting in withdrawal from the study) are considered to be AEs.

This includes the following:

- AEs not previously observed in the subject that emerge during the protocol-specified AE reporting period (see Section 12.1), including medical triggers resulting in an HAE attack. Emotional stress will not be considered an AE unless it results in a medical diagnosis or requires medical treatment.
- Findings from protocol-mandated interventions. This can include laboratory assessments performed in the course of the clinical trial. AEs should only be reported if the abnormalities are changes from baseline and are clinically significant as described above.
- Pre-existing medical conditions (other than the condition being studied) judged by the investigator to have worsened in severity or frequency or changed in character during the protocol-specified AE reporting period

An adverse reaction is defined in Article 2(n) of Directive 2001/20/EC as follows: all untoward and unintended responses to a study drug/IMP related to any dose administered. The definition covers also medication errors and uses outside what is foreseen in the protocol, including misuse and abuse of the product. The definition implies a reasonable possibility of a causal relationship between the event and the study drug/IMP. This means that there are facts (evidence) or arguments to suggest a causal relationship.

For the purposes of this protocol, HAE attacks and their associated symptoms will not be defined as AEs, unless they meet the criteria for a SAE. HAE attacks and associated symptoms will be recorded in the subject's diary. The events that may trigger a HAE attack such as an infection or trauma are considered AEs and should be reported as such.

Surgical procedures should not be reported as AEs. The condition for which the surgery is required should be reported as the AE, if it occurs or is detected during the study period. Planned

surgical measures permitted by the clinical study protocol and the conditions(s) leading to these measures are not AEs, if the condition(s) was (were) known before the start of study treatment. In the latter case the condition should be reported as medical history.

Adverse events are designated as "nonserious" or "serious."

#### 12.1.1.2. Serious Adverse Event

A SAE is an adverse event/reaction that results in any of the following outcomes:

- Death
- Is life-threatening (subject is at immediate risk of death at the time of the event; it does not refer to an event that hypothetically might have caused death if it were more severe)
- Requires subject hospitalization (formal admission to a hospital for medical reasons) or prolongation of existing hospitalization
- Results in persistent or significant disability/incapacity (i.e., there is a substantial disruption of a person's ability to carry out normal life functions)
- Is a congenital anomaly/birth defect

Important medical events that may not result in death, are not life-threatening, or do not require hospitalization may be considered a SAE when, based upon appropriate medical judgment, they may jeopardize the subject's health or may require medical or surgical intervention to prevent one of the outcomes listed in this definition. For this study, examples of such events may include allergic bronchospasm requiring intensive treatment in an emergency room or at home, blood dyscrasias, or convulsions that do not result in subject hospitalization.

Overdose will be considered an SAE only if any of the seriousness criteria are met. Any clinical complication in association with the overdose should be reported as an AE or SAE (as applicable) along with the overdose (see Section 12.2.2). Details of signs or symptoms, clinical management and outcome should be reported, if available. Overdose without associated signs or symptoms should not be recorded as AEs but should be recorded as protocol deviations.

BioCryst also considers abortions, whether elective or spontaneous, fetal demise, and still births as SAEs.

## 12.1.1.3. Adverse Events of Special Interest

For this protocol, nonserious treatment-emergent rashes will be considered events of special interest. This event in and of itself will not be considered serious unless it meets the criteria above. Events of rash regardless of severity or suspected relationship to study drug/IMP must be reported to the Sponsor Medical Monitor as described in Section 12.1.5.1. Management of rash possibly, probably or definitely suspected to be related to study drug/IMP, is provided in Section 12.2.1.

# 12.1.2. Method, Frequency, and Time Period for Detecting Adverse Events and Reporting Serious Adverse Events

Reports of all AEs and SAEs, regardless of Investigator attribution, are to be collected from the time of signing of the informed consent until the post –attack 3 visit of the study drug phase. All AEs and SAEs are to be reported on the AE CRF. For subjects who continue in the optional observational substudy, **only** those AEs deemed possibly, probably or definitely related to the previously taken study drug need to be recorded on the AE CRF. These AEs will be recorded in the same manner and include the same information as AEs during the study phase.

AEs should be documented on eCRFs as Investigators become aware of them. AEs are to be followed until the event resolves. If an event is ongoing at the last follow-up visit in the main study, Grade 1 and 2 events do not need to be followed if the event is deemed unlikely to be related or not related to study drug/IMP (see Section 12.1.3 for AE grading). For all Grade 3 and 4 events or events deemed possibly, probably or definitely related to use of study drug/IMP, the event should be followed until the AE is resolved or the subject is in a clinically stable condition with regards to the AE.

The Investigator shall report all SAEs immediately to the Sponsor by communicating with the Medical Monitor (phone or email) and by submission of an SAE report form via fax or email, and entering the event onto the AE eCRF within 24 hours of their knowledge of the event (see Section 12.1.5). The SAE report form is a detailed, written report on the SAE provided by the Sponsor or designee. The Investigator should follow all unresolved SAEs observed during the study until they are resolved, or are judged medically stable, or are otherwise medically explained.

The Investigator should attempt, if possible, to establish a diagnosis based on the presenting signs and symptoms. In such cases, the diagnosis should be documented as the AE and not the individual sign/symptom. If a clear diagnosis cannot be established, each sign and symptom must be recorded individually. Once a diagnosis is made during evaluation or treatment, the Investigator will update the AE record with this diagnosis. The immediate and follow-up reports shall identify subjects by unique code numbers assigned to the latter to ensure that the Sponsor shall have the necessary information to continuously assess the benefit-risk profile of the study drug/IMP in clinical trial.

# 12.1.3. Definition of Severity

All AEs will be assessed (graded) for severity and classified using the Division of Microbiology and Infectious Diseases (DMID) criteria for grading AEs (see Appendix 15.1). Any AEs not covered by the DMID criteria will be assessed and classified into 1 of 4 clearly defined categories as follows:

Protocol BCX7353-202 Version 4.0

# BioCryst Pharmaceuticals, Inc. CONFIDENTIAL

BCX7353

(Grade 1): Transient or mild symptoms; no limitation in activity; no intervention Mild:

required. The AE does not interfere with the participant's normal functioning level. It

may be an annoyance.

Moderate: (Grade 2): Symptom results in mild to moderate limitation in activity; no or minimal

intervention required. The AE produces some impairment of functioning, but it is not

hazardous to health. It is uncomfortable or an embarrassment.

(Grade 3): Symptom results in significant limitation in activity; medical intervention Severe:

may be required. The AE produces significant impairment of functioning or

incapacitation.

Life-(Grade 4): Extreme limitation in activity, significant assistance required; significant threatening:

medical intervention/therapy required to prevent death, hospitalization or hospice care

probable.

#### 12.1.4. Definition of Relationship to Study Drug (Investigational Medicinal Product)

The Investigator or medically qualified designee must review each AE and make the determination of relationship to study drug/IMP using the following guidelines:

**Not Related:** The event can be readily explained by other factors such as the subject's underlying

medical condition, concomitant therapy, or accident, and no temporal relationship

exists between the study drug/IMP and the event.

**Unlikely:** The event does not follow a reasonable temporal sequence from drug administration

and is readily explained by the subject's clinical state or by other modes of therapy

administered to the subject.

There is some temporal relationship between the event and the administration of the **Possibly** 

**Related:** study drug/IMP and the event is unlikely to be explained by the subject's medical

condition, other therapies, or accident.

**Probably** The event follows a reasonable temporal sequence from study drug/IMP

administration, abates upon discontinuation of the study drug/IMP, and cannot be **Related:** 

reasonably explained by the known characteristics of the subject's clinical state.

**Definitely** The event follows a reasonable temporal sequence from study drug/IMP

**Related:** administration, follows a known or suspected response pattern to the study drug/IMP,

is confirmed by improvement upon stopping the study drug/IMP (dechallenge), and

reappears upon repeated exposure (rechallenge, if rechallenge is medically

appropriate).

# 12.1.5. Reporting Serious Adverse Events and Suspected Unexpected Serious Adverse Reactions

Any SAE must be reported by phone or email to the Sponsor Medical Monitor and in writing via email or fax using the SAE/Event of Special Interest report form within 24 hours of the Investigator's awareness of the SAE. In addition, all SAEs must be recorded on the AE eCRF in real time. All additional follow-up evaluations of the SAE must be reported to BioCryst or its designee as soon as they are available. The SAE report forms should be sent to the following email addresses or fax numbers:

[name], Medical Monitor Cell number (24 hours) [contact]

Email: [contact]; [contact]

Safety [contact]

Immediate reporting should allow BioCryst to take the appropriate measures to address potential new risks in a clinical trial. Therefore, the initial report should be submitted by the Investigator within a very short period of time and under no circumstances should this period exceed 24 hours following awareness of the SAE.

The follow-up report should allow BioCryst to determine whether the SAE requires a reassessment of the benefit-risk profile of the study drug/IMP in clinical trial, if the relevant information was not already available and provided in the initial report.

Investigators or designees at each site are responsible for retaining copies of all suspected unexpected severe adverse reaction (SUSAR) reports (initial and follow-up) and other safety information (eg, revised IB) in their files.

BioCryst or its designee will submit all SUSAR reports (initial and follow-up) or other safety information (eg, revised IB) to the IEC and central IRBs.

BioCryst shall ensure that all relevant information about SUSARs that are fatal or life-threatening is recorded and reported as soon as possible to all competent authorities, and to the IECs, and central IRBs, in any case no later than 7 calendar days after knowledge by BioCryst of such a case, and that relevant follow-up information is subsequently communicated within an additional 8 days. All other SUSARs shall be reported to the competent authorities concerned and to the IECs/IRBs concerned as soon as possible but in no case later than 15 calendar days of first knowledge by BioCryst. BioCryst or designee shall also inform all Investigators.

# 12.1.5.1. Reporting Events of Special Interest

Although not an SAE, all events of treatment-emergent rash regardless of severity or relationship to study drug/IMP must be reported by phone or email to the Sponsor Medical Monitor and in writing via email or fax using the SAE/Event of Special Interest report form within 24 hours of the Investigator's assessment of the event. In addition, the event must be recorded on the AE eCRF in real time. All additional follow-up evaluations of the event must be reported to BioCryst or its designee on the form as soon as they are available. The SAE/Event of Special Interest report form should be sent to the following email addresses or fax numbers:

[name], Medical Monitor Cell number (24 hours) [contact]

Email: [contact]; [contact]

Safety [contact]

Immediate reporting should allow BioCryst to take the appropriate measures to address potential new risks in a clinical trial. Therefore, the initial report should be submitted by the Investigator within a very short period of time and under no circumstances should this period exceed 24 hours following awareness of the event. In addition, the report form will allow a full clinical description and information regarding the evaluation that cannot be reported in the EDC.

The follow-up report should contain information about the clinical course, medical evaluation, photographs, biopsy, and laboratory results.

## 12.1.6. Pregnancy

Any female subject who becomes pregnant during the course of the study should have study drug/IMP discontinued immediately and must be followed through the end of the pregnancy. While pregnancy is not considered an AE, all cases of fetal drug exposure via the parent as a study participant (including partners of study participants) are to be reported immediately to BioCryst or its designee. Consent from study partners will be obtained prior to reporting any details of the pregnancy. Information related to the pregnancy must be given on a "Pregnancy Confirmation and Outcome" form that will be provided by the Sponsor or its designee so that the pregnancy may be followed and an outcome determined. Any AEs or SAEs experienced by a pregnant subject are to be reported as directed above in Section 12.1.2 and Section 12.1.5. Any complications reported in a subject's pregnant partner should be reported on the Pregnancy Confirmation and Outcome form. All pregnancies must be followed to outcome which occurs when an infant is delivered (live or still born), there is fetal demise, or there is an abortion (spontaneous or induced). Abortion (spontaneous or induced), fetal demise, and still birth along with congenital abnormalities in the newborn, should be reported as separate SAEs.

#### 12.1.7. Serious Breaches

It is the responsibility of the Sponsor to notify the competent authority of any serious breach which is likely to effect, to a significant degree, the safety or mental integrity of the subjects of the study or the scientific value of the study. All serious breaches will be notified to the relevant

competent authority within 7 days. The reporting to the Sponsor will be performed by the party who suspects the serious breach.

# 12.1.8. Emergency Procedures

Access to study drug/IMP assignment will be available immediately if the Investigator deems it necessary to break the study blind in the interest of a subject's medical safety. In addition, the blind may be broken in case of a medical emergency, to meet regulatory reporting obligations, or if warranted during scheduled safety reviews. Where medically appropriate, the Investigator will contact the Sponsor Medical Monitor to discuss unblinding of the subject; however, the final decision to break the treatment code in emergency situations resides solely with the Investigator. Detailed instructions for immediate unblinding in the interactive web response system used by the site to randomize a subject will be provided.

# 12.2. Toxicity Management

The Investigator (or qualified designee) will grade clinically significant events and laboratory abnormalities (if considered AEs) according to that detailed in Section 12.1.3. Grade 3 and 4 clinically significant laboratory abnormalities should be confirmed by repeat testing and before any contemplated study drug/IMP discontinuation, unless such a delay is not consistent with good medical practice.

In the event that 2 subjects experience similar Grade 3 or 4 treatment-emergent laboratory abnormality or AE that is suspected to be IMP related as determined by the Investigator and not otherwise physiologically explained, a DMC meeting will be immediately convened by the Sponsor. Based on the data presented, a decision will be made as to whether to halt the study, to continue dosing, or to continue dosing with provisions introduced into the protocol via substantial amendment.

## 12.2.1. Rash

Management of rash should be based on best medical practice and address the subject's presentation. If a subject experiences a Grade 3 or 4 rash suspected to be due to study drug/IMP, the subject should have study drug/IMP stopped as per Section 8.3.2.2.

In the event that 2 subjects experience a rash that is suspected to be study drug/IMP related as determined by the Investigator and not otherwise physiologically explained, a DMC meeting will be convened by the Sponsor. Based on the data presented, a decision will be made as to whether to halt the study, to continue dosing, or to continue dosing with provisions introduced into the protocol via substantial amendment.

Special evaluation of drug rash is required as per Section 12.1.1.3 and special reporting is described in Section 12.1.5.1.

#### 12.2.2. Overdose

To date there is no experience with overdose of oral BCX7353. Only one dose of study drug is provided to each subject at a time, so overdose is not of concern in the study. The maximum dose to be administered in the current study is 750 mg. Single doses of up to 1000 mg, 7 days of

dosing up to 500 mg/day, and 14 days of dosing with 350 mg/day revealed no clinically significant safety concerns in healthy subjects in Study BCX7353-101.

# 12.3. Data Monitoring Committee

An independent Data Monitoring Committee (DMC) will review safety data on an as needed basis. The DMC will be convened upon meeting the criteria listed in Section 12.2 or at other times as requested. A separate DMC charter, maintained in the trial master file, will describe membership, roles, timing of DMC review, and responsibilities of the DMC members.

# 13. STATISTICS

# **13.1.** Sample Size Considerations

Given the exploratory nature of this study, the sample size was not chosen based on statistical considerations, but rather to provide preliminary safety and efficacy data on BCX7353 in subjects with HAE when treated in accordance with this study.

# 13.2. Hypothesis Testing

An analysis may be conducted during Part 1, using the Heybittle-Peto boundary for significance, to determine whether there is a clinically important treatment effect with BCX7353. The endpoint for this analysis is the proportion of subject attacks with a stable or improved VAS at 4 hours postdose in the full analysis set. The null hypothesis evaluated  $(H_0)$  is that the proportion of subject attacks treated with BCX7353 with stable or improved VAS at 4 hours postdose is the same as proportion of subject attacks treated with placebo with stable or improved VAS at 4 hours postdose (i.e., no treatment difference). The alternative hypothesis  $(H_1)$  is that the proportion of subject attacks treated with BCX7353 with stable or improved VAS at 4 hours postdose is greater than the proportion of subject attacks treated with placebo with stable or improved VAS at 4 hours postdose (i.e., treatment difference).

# 13.3. Statistical Methods

A detailed statistical analysis plan (SAP) will be developed and finalized prior to database lock. The SAP will describe the methods of analyses/summaries, including all endpoints, time points, populations, missing data, etc. Any deviation from the analyses outlined in the SAP will be described in the final clinical study report.

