#### 7.1.1. Enrollment and Analyses

Up to 36 subjects will be enrolled in Part 1. Upon full enrollment, enrollment into Part 2 of the study (maximum of 12 subjects) may immediately commence. Likewise, Part 3 (n = up to 12) may immediately commence upon enrollment of Part 2.

Following the 12th subject completing Part 1, the treatment effect may be estimated. The predefined endpoint, determined by the Haybittle-Peto method, is the proportion of subjects with a stable or improved composite VAS at 4 hours postdose of an HAE attack. A Haybittle-Peto boundary of p < 0.001 is considered clinically significant.

If the Haybittle-Peto analysis is run and the boundary is not crossed with 12 subjects, the treatment effect may be re-estimated with cumulative data after each treated attack in accordance with the fully sequential analysis method. At each evaluation, the treatment effect may be assessed using the Haybittle-Peto boundary (p < 0.001).

Alternatively, if the boundary is not crossed with 24 subjects enrolled or the Heybittle-Peto analyses are not performed, treatment differences may be assessed using available data in Parts 1, 2 and 3 in order to plan subsequent studies.

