#### 8. SELECTION AND WITHDRAWAL OF SUBJECTS

# 8.1. Number of Subjects

Up to 36 evaluable subjects with Type 1 or 2 HAE are planned to be enrolled in Part 1, up to 12 evaluable subjects in Part 2, and up to 12 evaluable subjects in Part 3. An evaluable subject is one who treats 3 attacks with study drug and for which there is diary information recorded for each treated attack.

Subjects who complete Part 1 will not be eligible to participate in Parts 2 or 3. Likewise, subjects who complete Part 2 will not be permitted to participate in Part 3.

Subjects who prematurely withdraw from the study may be replaced at the Sponsor's discretion. Any subject who has withdrawn from the study as a result of a treatment-emergent AE (regardless of severity or causality) may not be replaced.

The following inclusion and exclusion criteria will be used to screen subjects for the study.

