# 9.3. Blinding and Randomization

## 9.3.1. Blinding

This is a double-blind study. As such, study drug treatment sequence will be blinded to the Investigator, study staff, study subjects, and clinical research organization (CRO) staff. Sponsor employee(s) not regularly interacting with the clinical sites will also be blinded to the treatment sequence of individual subjects, with the exception of Sponsor staff responsible for managing clinical supplies.

The project statistician performing the analyses with a Haybittle-Peto boundary for significance may become unblinded after the 12th subject completes Part 1. Sponsor employees may be unblinded at the same time or at any point thereafter.

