#### 9.3.2. Randomization

Up to 36 subjects will be sequentially enrolled into Part 1 of the study and randomized to receive a treatment sequence containing one of the following:

- Treatment A: Single oral dose of BCX7353 750 mg (Part 1)
- Treatment B: Single oral dose of placebo

Initially in Part 1, 12 subjects will be randomized 1:1:1 to the following treatment sequences (n = 4 subjects per treatment sequence):

• Sequence 1:  $A \rightarrow B \rightarrow A$ 

• Sequence 2:  $B \rightarrow A \rightarrow A$ 

• Sequence 3:  $A \rightarrow A \rightarrow B$ 

Note: Treatment  $A^1$  = single oral doses of BCX7353 750 mg in Part 1; Treatment  $A^2$  = single oral doses of BCX7353 500 mg in Part 2; and Treatment  $A^3$  = single oral doses of BCX7353 250 mg in Part 3.

A subject will be randomized to a treatment sequence at or prior to the Baseline visit.

Subject randomization will occur only after the following steps have been completed and reviewed by the Sponsor:

- a) The following data is provided to the Sponsor: qualifying historical HAE attack data, concomitant and past medications, C1INH function and C4 level (or SERPING-1 mutation), and the data collected on the HAE medical and medication history form. AND
- b) A site-documented screening HAE attack has occurred (i.e., subject phones Investigator prior to the attack and approximately 4 hours later)

For the documented attack, the completed diary does not have to be collected to randomize a subject; however, the on-call Investigator (or designee) should ensure the subject has competently completed the attack diary.

Specific details of the randomization and kit shipment processes will be communicated to the sites.

Study drug will be dispensed to subjects in a quantity sufficient for the treatment of one acute attack. Each subject will be assigned study drug a total of 3 times, which will be dispensed at Baseline and at the clinic visits following the first and second attack.

Information on unblinding in the event of a SAE is provided in Section 12.1.8.

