# 13.3.3. Analysis of Efficacy Variables

As this is the first study of BCX7353 in the treatment of acute attacks, the analysis of attack resolution will be described in a number of ways which will be fully detailed in the SAP. The endpoint that may be utilized to first examine efficacy is the proportion of subject attacks with a stable or improved VAS at 4 hours postdose in the full analysis set. The number and proportion of subject attacks with a stable or improved VAS at 4 hours postdose will be summarized by treatment group. Attacks that require standard of care medication prior to the 4 hour time point will be considered as failure (i.e., not having a stable or improved VAS at 4 hours postdose). To assess treatment differences, a logistic mixed effect model including treatment, period and sequence as fixed effects, and subject within sequence as a random effect will be utilized. Other binary endpoints will be analyzed in a similar manner.

The 3-symptom composite VAS and its associated changes from baseline will be summarized for each attack by time point and treatment group. Treatment differences in the change from baseline values at each time point will be assessed with a mixed effect linear model with factors for treatment, period, sequence, and baseline value as fixed effects, and subject within sequence as a random effect. Analyses of other continuous variables will be analyzed in a similar manner.

The time to use of standard of care medication will be estimated using the method of Kaplan-Meier. For each attack, subjects who do not use standard of care medication will be censored at the end of the attack observation period (i.e., 24 hours). Treatment differences will be assessed using an appropriate proportional hazards model. Analyses of other type to event variables will be analyzed in a similar manner.

Location of attacks, duration of attacks, and number of acute HAE medications administered will be summarized for each treatment group.

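### The SAP is due only by database lock, yet the statistician and sponsor staff may be unblinded after the 12th Part 1 subject, so rules still open can be set with results known

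*Protocol*

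**What the plan says.** **Timing and content of the SAP.** Protocol 13.3 states: "A detailed statistical analysis plan (SAP) will be developed and finalized prior to database lock". On content it adds: "The SAP will describe the methods of analyses/summaries, including all endpoints, time points, populations, missing data, etc". Section 13.3.3 defers further detail: "the analysis of attack resolution will be described in a number of ways which will be fully detailed in the SAP".

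**Unblinding.** Protocol 9.3.1 states: "The project statistician performing the analyses with a Haybittle-Peto boundary for significance may become unblinded after the" 12th subject completes Part 1. It continues: "Sponsor employees may be unblinded at the same time or at any point thereafter". The section does not say which sponsor roles this covers, and it does not separate the unblinded statistician from the authors of the SAP.

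**Repeated looks.** If the boundary is not crossed with 12 subjects, Protocol 7.1.1 says "the treatment effect may be re-estimated with cumulative data after each treated attack in accordance with the fully sequential analysis method".

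**The supplied SAP.** It covers Study BCX7353-302, a Phase 3 prophylaxis trial. It therefore does not show when the SAP for this study (BCX7353-202) was or will be finalised.

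**The concern.** A SAP protects against data-driven choices only if it is closed before its authors can see results by treatment. Here the two clocks are not linked. Unblinding may begin at the 12th completer, while the SAP may stay open until the end of the study. Someone who knows the treatment results could then write rules that affect them, without breaching the protocol.

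The study is exploratory, but its results carry weight. Section 5.4.2 treats crossing the boundary as convincing evidence of effect, and 7.1.1 and 13.3.6 say treatment differences may be used to plan later studies. An effect estimate shaped by choices made after unblinding would carry its optimism into the dose selection and sample size of those studies.

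**Working it through.** The plan gives no sample size or power figure to reproduce (13.1 says size was not set on statistical grounds). The check compares sections and counts attacks.

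**1. Order of events that the text permits**
- The 12th Part 1 subject completes (9.3.1, 13.3.6).
- The statistician may be unblinded; sponsor employees may be unblinded then or later (9.3.1).
- The effect may be re-estimated after each further treated attack (7.1.1).
- The SAP is due before database lock (13.3). The protocol describes no separate lock or freeze for the interim look.

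No section places SAP sign-off before the second step.

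**2. How much can be known while the SAP is open**

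Inputs: 3 treated attacks per subject, 2 active and 1 placebo (9.1); at most 36, 12 and 12 evaluable subjects in Parts 1, 2 and 3 (8.1).
- First permitted unblinding, completers only: 12 × 3 = 36 attacks, of which 12 × 2 = 24 active and 12 × 1 = 12 placebo.
- Part 1 maximum: 36 × 3 = 108; 36/108 = 33%.
- Study maximum: (36 + 12 + 12) × 3 = 180; 36/180 = 20%.

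With looks after each further attack, the known share can keep rising before the SAP is due.

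**3. What the protocol already fixes**
- Ten efficacy endpoints, several with numeric definitions (7.2.1).
- The 4-hour stable-or-improved VAS endpoint and the hypotheses of the optional look (13.2), with its p < 0.001 threshold (13.3.6).
- The FAS, named as primary for efficacy, and the safety population (13.3.1.1, 13.3.1.2).
- The logistic and linear mixed models with their terms, early standard-of-care use counted as failure, and 24-hour censoring for time to standard of care (13.3.3).

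**4. What remains open**
- *Missing data.* No analysis method is stated. This reaches the endpoint of the look itself. A subject asleep at 4 hours completes that entry on waking (11.2.2.1.2), and no rule says whether such an entry counts as 4-hour data. The same section lets the investigator's call form stand in as source for an empty diary field, but that is a source-data rule, not an analysis rule.
- *Placebo pooling.* Sections 7.1.1 and 13.3.6 foresee analyses using Parts 1, 2 and 3, but not whether placebo attacks are pooled. At full enrolment, the 24 active attacks at 500 mg (12 × 2) could be compared with 12 placebo attacks from Part 2 or with 36 + 12 + 12 = 60 from all Parts.
- *Time-to-event model.* Section 13.3.3 says only that a suitable proportional hazards model will be used. It does not give the covariates or say how several attacks in one subject are handled.
- *Emphasis.* None of the ten endpoints is labelled primary, and no multiplicity rule or final significance level is given.

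**The case against.** The strongest reply is that the protocol already carries the core of the analysis, as listed above. A reader might infer from 13.3 that endpoints and populations themselves can be chosen late. The documents do not support that. The endpoint list and populations are set, and the 4-hour VAS is clearly the lead endpoint: it is listed first, is named in 13.3.3 as the one that may be used first to examine efficacy, and is the only one tested against a boundary. What can move is emphasis among listed endpoints and the rules in step 4.

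A reader might also connect sponsor unblinding with two conduct provisions: "Subject randomization will occur only after the following steps have been completed and reviewed by the Sponsor" (9.3.2) and "Subjects who prematurely withdraw from the study may be replaced at the Sponsor's discretion" (8.1). Neither gives a convincing route to bias. Every subject receives both active and placebo, so deciding who enters does not unbalance the treatments. The FAS keeps all treated attacks, so replacing a subject deletes nothing. Section 8.1 also says subjects withdrawn for a treatment-emergent adverse event may not be replaced.

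A third temptation is to size the problem by the chance of a false positive among ten endpoints. That would measure multiplicity, which would be the same under a SAP signed on day one without a hierarchy. It would also need a final significance level and correlations between endpoints that this protocol does not state.

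Other replies stand in part:
- Unblinding and the looks are optional, and the study is declared exploratory. This lowers the consequence but does not close the gap.
- Subjects, investigators, site staff and CRO staff are blinded under 9.3.1, outcomes are recorded by subjects, and staff may not enter attack information in diaries (11.2.2.1). Outcome recording is therefore largely protected; the exposure is in the analysis rules.
- Section 13.3 promises that deviations from the SAP will be reported. That does not help when the choice is written into the SAP after unblinding, because it is then not a deviation.
- Database lock is an outer limit, and the SAP may have been signed well before any look. The documents cannot show this either way.

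**Conclusion.** The point holds as a timing gap: the protocol allows specific analysis rules to be settled after treatment results are known, and nothing in the supplied documents prevents it. The rules affected are missing data (including 4-hour entries made on waking), pooling of placebo across Parts, the time-to-event model and the emphasis among listed endpoints.

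Its size can be given only as exposure: 36 attacks by treatment at the first permitted unblinding, one third of the Part 1 maximum and one fifth of the study maximum, and potentially more at each later look. This assumes that the optional unblinding is used, that enrolment reaches its caps, and that only the 12 completers' attacks are counted. The resulting bias cannot be estimated from the documents.

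The finding does not show that any choice was made with results in hand, that the endpoints are free to change, or that randomisation or replacement is biased. It is a defect worth correcting because the correction is simple, not because the study's main comparison is undefined.

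**What to change.** In Protocol 13.3, replace the database-lock deadline with two requirements:
- The SAP for BCX7353-202 is signed and dated before any unblinded look, at the latest when the 12th Part 1 subject completes. It states the missing-data rules (including how entries made on waking are treated), whether placebo attacks are pooled across Parts, the time-to-event model and the order of emphasis among the endpoints.
- Any analysis specified after unblinding is labelled post hoc in the study report.

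The sponsor's SAP for Study BCX7353-302 already follows this order: its Section 2 has the plan finalised before lock for the interim analysis, and its Section 5.2 has unblinding follow the database freeze for the Part 1 analysis.

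The only cost is writing the same SAP earlier. Restricting which sponsor staff may be unblinded under 9.3.1 is optional and not needed for this fix.
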